#### **D. Screening**

The Caregiver Screening Form will be used to determine if the caregiver meets study inclusion criteria. This form may be completed in-person, or via phone or video call. If study criteria are met and the family caregiver agrees to participate, they will be offered several potential dates and times for scheduling verbal consenting and data collection. In preparation for the appointment, a copy of the Study Consent Information Document will be emailed or mailed to potential participant in advance of consenting for them to read in advance of consenting and to keep a copy for their records. This email will contain the Study Introduction Note and the Study Welcome Video (see scripts in appendix), and the Caregiver Study Information Document, Mental Health Resources Sheet, and Zoom® Instructions will be attached (see appendix). Data collected during the screening process such as family caregiver type may be included as study data from participants once consented.

Participants will verbally agree to participate in the study. Prior to establishing the peers, the Participant Intake Form (see appendix) will be completed to ensure the best matches based on similar qualities. This form will also include their preferences for receipt of email/text/phone call communication.

#### **E. Consenting**

All data from study participants will be collected following IRB approval of study procedures. Each study participant will provide a verbal informed consent prior to all data collection. Consent procedures will be conducted remotely allowing flexibility for participation. Potential caregivers will be emailed (using Caregiver Recruitment Script) the Caregiver Consent Information Document, Mental Health Resources Sheet, Zoom® Instructions, along with a copy of the IRB-approved Study Flier ahead of the consenting appointment. A reminder text/phone call/email will be placed/sent at least 1 day prior to the appointment using the Text Message or Email Scripts – see appendix). The research team member will meet with potential participant via phone or video call. The Caregiver Consent Information Document will be read aloud by the research team member, or the participant may choose to read it for themselves before providing verbal consent. Time will be allowed for the participants to ask questions and responses will be provided. Once all information has been clarified, the research team member will ask the following questions and their responses documented in REDCap by the research team member:

In order to provide your verbal consent, can you please answer the following questions:

1. "Do you agree to participate in the Pair 2 Care: Peer Support for Caregivers of African Americans Living with Dementia Study? YES or NO
2. "Is it okay for me to record the audio during the interview?" YES or NO

3. "When the study is completed, would you like to receive a copy of the study results?"  
YES or NO
4. "Would you like to be contacted about the chance to be in other research studies?" YES or NO

A response of 'Yes' must be provided for question #1 for the participant to be enrolled.

Once the participant is enrolled in the study, they will be sent a welcome email/text containing the study introduction video developed using the Study Introduction Video Script (see appendix) recorded by the PI. Alternatively, a brief welcome letter will be mailed (see appendix for Study Welcome Video>Note).

#### Consent Addendum

Mentors will be invited to complete an optional 1-hour audio-recorded individual interview at the end of the study (Month 6 or 7) about their experience as a mentor in the study. This interview will be audio recorded using two voice recorders. During the interview, they will have the option to choose not to answer any question that they do not wish to answer. The interview will be completed over the telephone or video call. Prior to the mentees completing the interview, mentors will be provided a copy of the consent addendum (see appendix) via mail and/or email using the Consent Addendum Email Script (see appendix). The following questions will be asked to obtain verbal consent prior to completing the interview:

1. "Do you agree to complete the optional mentor interview for the Pair 2 Care Study?" YES or NO
2. "Is it okay for me to record the audio during the interview?" YES or NO

A response of Yes" must be provided for question #1 in order for the interview to be completed.

At the beginning of the study, we will ask caregivers to provide us their phone number so we can add it to our participant communication platform. During the study, we will use Twilio integrated into REDCap to communicate with participants via text messaging. Participants will not pay any additional charges for this service over and above what they normally are charged by their mobile network provider for sending and receiving text messages or transmitting/receiving any data. Twilio is completely integrated into the OSU version of REDCap and does not require use of a separate app to communicate with participants. All participant information will be kept within the REDCap platform. Participants are unable to respond to text messages sent via Twilio. Only trained study staff will be able to access the REDCap project.

#### **F. Mentor Training**

Prior to engaging with their current caregiver mentee, former caregivers will complete up to two 1-hour virtual training sessions either individually or via group session(s) over Zoom® (see appendix for Mentor Training Slides). This training will include video-recorded communication scenarios using culturally congruent actors for four exemplar scenarios: Training video script #1 - Support for Caregivers, training video script #2 – Near End-of-Life Scenario, training video script #3 - Happy Peer Connection, and training Video Script #4 – Long-term Care Decision Making

(see appendix). A Black-owned media company such as, SpencerHigherforMedia® will be hired to review scripts and for talent acquisition to support cultural congruency. Manipulation checks will be conducted using verbal questions posed by the study team using following training sessions (see Mentor Training Manipulation Checks Survey). This will include “what if” scenarios to ensure understanding of content delivered. If responses reveal that former caregivers are not receiving the intervention as intended, we will immediately reassess, discuss with the FamCAB, and may schedule an additional training session, if needed. The additional one-on-one training sessions may be scheduled to review previously covered information with former family caregivers and answer any questions as needed. A brief 1–2-page Mentor Training Summary Sheet (see appendix) will be provided at the end of the training sessions once the mentor is paired with their mentee. While former caregiver (mentee) training may be completed in group settings or individually, no surveys, questionnaires, or interviews, etc. will be collected on a group setting. Following the training, mentors will complete the Mentor Training Evaluation Form (see appendix) via text or email to provide feedback on the training session(s) Table 1 outlines former caregiver training activities. Emails and or texts will be sent prior to mentor trainings using the Text Message or Email Script. Once the mentor training is completed, a certificate of completion (see appendix) will be sent to each via mail and email using the Mentor Training Certificate Email Script (see appendix). Mentors will be able to meet with a research team member as needed.

**Table 1: Mentor Training Activities**

Day	Activity
1	
 
• Explain purpose of Pair 2 Care Intervention
 
• Introduce ice breaker conversations - demonstrate and practice
 
• Review meaning of palliative care and end-of-life care-related terminology
 
• Discuss rules for engagement with current caregivers e.g., method, frequency, duration
 
• Review topics to be discussed – provided a 1–2-page summary format
 
• Review and provide and handout of discussion topics with conversation starters and topic schedule
 
• Model practice conversations with tips provided using training videos
 

2	
 
• Review of Day 1 activities
 
• Practice icebreaker conversations
 
• Practice peer interactions through role play
 
• View and discuss “what if” scenarios including training videos e.g., if current/former caregiver become emotional, reporting to study staff
 
• Summarize training and intervention purpose
 
• Questions and answers
 

## G. Data Collection

All data will be collected remotely by a study team member using REDCap software. Data collection will be scheduled at a time that is convenient for the participants via telephone or video conference call. Options for during the days, evenings, and weekends may be offered to be flexible in meeting the needs of the study participants. A 2-week window will be given around each data collection timepoint for data collection to take place. The appointment reminders will be used to send reminder email, phone call, or text messages for all study appointments and weekly nudges/reminders using the Text Message or Email Scripts. A weekly text/email/reminder phone call message may be used to: 1) thank participants for being in the study, 2) remind mentees and mentors to connect, and/or 3) remind mentees to complete their Weekly Mentee Interaction Assessment Response Form.

**Pairing of Mentors and Mentees:** Once mentor training session(s) are completed, mentors and mentees will be paired based on similar qualities such as caregiving relationship and gender identity based on information provided on the Caregiver Intake Form. Mentors may be assigned an additional mentee. A virtual introduction of current and former caregiver pairs will be made by a study team member using the Peer Introduction Meeting with Research Team Member Agenda (see appendix).

Each pair will complete at least five virtual face-to-face (video) interactions and at least 10 other interactions either via phone call, email, or text messaging over the 6-month time period based on average timeframe and number of interactions for similar research studies. A weekly check-in via text, email or phone call from a research team member will be completed to confirm and document mode and frequency of interactions as well as topics discussed (see Table 2) using the Weekly Mentee Interaction Assessment Response Form (see appendix). It includes indication for if the form was completed directly by the mentee via text message or email link or of completed by a research team member with them over the phone. This information will be tracked such as on a peer interaction log. These records will serve as manipulation checks to determine if the suggested topics are being discussed. Caregiver interactions will be flexible i.e., scheduling, duration, content, medium (telephone vs video).

**Table 2: Peer Discussion Topics**

Category	Topics
Caregiver and care recipient needs	accessing/selecting healthcare providers, attending doctor visits, attending worship services, coronavirus pandemic/endemic, exercise, faith, family dynamics, finances, healthcare decision making, mental health, nutrition, physical health, sleep, social activities, spirituality
Caregiver needs	managing multiple responsibilities, respite care, self-care, social support, work (inside and outside of the home)
Care recipient needs	activities of daily living, attending public events, adult daycare, advance care planning, assistive devices, coping with dementia-related behavioral symptoms, end-of-life planning, financing care, hospitalizations, mobility, nursing homes, nutrition, palliative care, hospice, support services/resources, skin care, urinary incontinence

**Measurement / Instrumentation:** Demographic data (e.g., age, gender, caregiving relationship) will be collected from all caregivers using the respective mentor and mentee demographic form (see appendix). State anxiety (Spielberger State Anxiety Inventory - STAI-S), depression (Center for Epidemiological Studies – Depression - CES-D), quality-of-life (Caregiver-Targeted Quality of Life – CGQOL), self-efficacy for surrogate decision making (Surrogate Decision Making Self-Efficacy Scale - SDM-SES), social support (Medical Outcomes Study Social Support Survey – MOS SSS), and intent to use palliative care/hospice (Mentee Palliative and Hospice Care Intent Form) data will be collected from mentees. Care recipient dementia stage (Quick Dementia Rating System - QDRS) and behavioral and psychological ADRD symptoms (Neuropsychiatric Inventory Questionnaire - NPI-Q) data will also be collected (see Table 3) (see appendix). Audio-recorded interviews (using the Mentee or Mentor Interview Guide – see appendices) conducted at one-month follow up via Zoom®, phone, or other virtual format with participants will characterize their experiences. Mentors will have the option to complete the interview at Month 6 or 7. Mentees will complete the interview at Month 7 (1 Month follow-up). Interviews will be conducted with participants to gather in-depth data on their Pair 2 Care Intervention experiences, including feedback on the likelihood of the intervention meeting the needs of African American ADRD caregivers. A member of the research team will connect with

former caregivers at the 3- and 6-month timeframe for feedback on how the mentoring process is going.

**Table 3: Data Collection by Timepoints**

Participant	Timepoint		
		Baseline 0-Month	Intervention 3 & 6 Months
Mentee	
 
1. Demographics
 
2. Participant Intake Form
 
3. Anxiety (STAI-S)
 
4. Depression (CES-D)
 
5. Dementia stage* (QDRS)
 
6. Behavioral and psychological ADRD symptoms** (NPI-Q)
 
7. Quality of life (CGQOL)
 
8. Self-efficacy (SDM-SES)
 
9. Medical Outcomes Study Social Support Survey (MOS SSS)
 
10. Mentee Palliative and Hospice Care Intent Form
 
	
 
1. Anxiety
 
2. Depression
 
3. Behavioral and psychological ADRD symptoms*
 
4. Quality of life
 
5. Self-efficacy
 
6. Social support
 
	
 
1. Anxiety
 
2. Depression
 
3. Behavioral and psychological ADRD symptoms*
 
4. Quality of life
 
5. Self-efficacy
 
6. Social support
 
8. Satisfaction and Appropriateness Survey
 
9. Acceptability Survey
 
10. Mentee Palliative and Hospice Care Intent Form
 
11. Mentee Interview Guide
 

Mentor	
 
1. Demographics
 
2. Participant Intake Form
 
	
 
1. Mentor Interview Guide (month 6 or 7 only)
 
	

\*Instrument completed by current caregiver about care recipient

Feasibility and acceptability will be determined by evaluating eligibility criteria, recruitment, and retention data (e.g., consent, drop out, refusal rates), protocol adherence, satisfaction, and appropriateness of the intervention for broader dissemination. The Satisfaction and Appropriateness Survey (see appendix) will be used to rate current caregiver intervention satisfaction and appropriateness. The Acceptability Survey (see appendix) will be used to assess acceptability of Pair 2 Care. This information will be collected on the Study Feasibility Log (see appendix). Benchmarks will be assessed per Table 4.

[figure not shown]
**Table 4: Feasibility and Acceptability Benchmarks**

Feasibility Benchmarks	
Eligibility Criteria	Criteria allows for enrollment goal to be met
Enrollment	Enrollment of 100% of participants in Year 1
Retention	Retain at least 70% of current and former caregivers
Intervention Training	At least 90% former caregivers complete training
Protocol Adherence	At least 80% adherence and keep record of suggested changes per FamCAB
Acceptability Benchmarks	
Satisfaction Survey	At least 70% completion rate; 80% satisfaction rate; 80% appropriateness rate
Interviews	80% interview completion

## H. Participant Incentives/Compensation for Time

Participants will receive a \$25 VISA® gift card and thank-you note (see Appendix - Text Message or Email Scripts) each time a set of surveys, mentee interview, mentor training is completed. Current caregivers (mentees) will complete surveys in the beginning, 3 months, 6 months, and 1-month follow-up. The 1-month follow-up will include an audio-recorded interview. Former caregivers (mentors) will complete surveys in the beginning, training, and 3-months and 6-months. You will receive a total of \$100 over the time of the study. See Figure 3 for Honorarium Distribution Plan. Data collection points will be tracked by the research team such as by using a data collection log. Gift cards will be delivered electronically via email or via mail (depending on their preference) using Virtual Incentives,® an OSU-reviewed portal. Participants will receive an email from Virtual Incentives® to select their preferred delivery method (electronic or mail). See appendix for sample view of Virtual Incentives® Reward Center Landing Page (see appendix) that includes a thank-you note (see appendix). Virtual Incentives® will be provided with participants name, mailing address, phone and/or email address. Virtual Incentives® will not share participants' information with others. This service is at no cost to the study participants. A security and privacy review was conducted by the OSU IT team to ensure compliance with all OSU guidelines and regulations. There will be no communications with study participants that are not study related and all participant identifiers will be destroyed after study completion. At the end of the study completion, each participant will be mailed a hand-written thank-you note in gratitude for their study participation.

**Figure 3: Honorarium Distribution Plan**

## I. Study Risks

Though this study poses minimal risks to participants, steps will be taken to ensure that participant risk remains minimal. As peer mentors are not health or healthcare experts, therefore, mentees will be reminded to seek advice from health experts for all health and safety issues (see Health Safety Protocol in appendix). This includes accessing 911 for all emergencies. If the mentor or mentee is unable to contact their mentor or mentee after four (4) attempts, they will be encouraged to cease and notify a study team member who will attempt to connect with the mentor or mentee. Participants with knowledge or concerns about health or safety issues will immediately report them to a study team member, who will report it to the study leader. The study leader is a

registered nurse and thus a mandated reporter and is therefore required by the State of Ohio to report abuse. The PI will notify the relevant authority for safety concerns and the research ethics board per protocol. Relevant health referrals and contact information will be provided directly to participants for health concerns. If found to be an unsafe environment, at the PI discretion, an event report will be made to make the decision to exit the study. The PI may be required to ask a participant to exit the study.

Discussions about death and dying may evoke feelings of related sadness related. Participants will be reminded that they can choose to end the interview at any time by telling the research team member and will be allowed to take breaks as needed. They will also be reminded that they can refuse to respond to a survey or interview question at any time if they are not comfortable or simply do not wish to respond simply by telling the interviewer that they do not wish to respond. Participants can also decide to drop out of the study at any time without penalization by telling the study team member. If a participant exits the study for any reason, their mentor/mentee may be allowed to continue participating if they choose to do so. The research team will thoroughly document the discontinuation of peer relationship, the remaining peer may be given the option to remain in the study, and their data analyzed to reflect this change in their engagement in the study. Their data may be analyzed separately from peers that complete the full study. Also, if the mentor-mentee relationship is not deemed a good match, attempts will be made by the research team, in collaboration with the PI, to address any concerns. It will be at the PI and research team discretion if it is unsafe for relationship and study participation to continue. If so, the peer participation in the study will end. The Study Exit Script will be used to convey, and study exit information. The PI in collaboration with the study team will determine if it is advisable to allow the participant(s) to remain in the study or not. Drs. [name] (PI) as a trained as registered nurse will be able to identify acute physical and/or psychological needs of the participants observed or reported and be able to make appropriate and timely referrals. If caregivers are thought to be experiencing any acute psychological or physical distress, they will be asked to visit their respective primary healthcare provider as well as offered access to community-based mental health resources or 911 services as outlined in the Health Safety Protocol. Participants will be instructed to contact the research team if any issues arise regarding the interaction/relationship with their peer. Any such challenge will be address with participants by the PI, if a solution is not possible or if the participant(s) choose, they will be allowed to exit the study (see appendix for Study Exit Script and Early Exit Form). If a caregiver chooses to leave the study or are asked to leave the study at any time for any reason, they will be asked not to be in contact with their mentor or mentee for any further study-related activities.

All electronic study data will be stored on a secure OSU College of Nursing research server. This includes recordings of demographic data, questionnaires, and interview transcripts. Each participant will be assigned a unique study identification alpha-numeric code. Only members of the study team will be able to link participants with study identification alpha-numeric code. Names, phone numbers, and mailing addresses will be stored separately from study alpha-numeric code numbers, recordings of verbal consents, study data, and interview transcripts. Data collected as part of this study will be stored in an established data repository per The OSU Policy and Procedures.

Contracted platforms such as Virtual Incentives© (secure gift card distribution service) maybe provided participants' names, mailing address, phone and/or email address. Study participants will be made aware of this during the consenting process. As part of their OSU security user agreements all external services used (Virtual Incentives, Rev, and Dedoose) will not share any participant information and they will delete this information at the end of the study. Interview

transcripts will be de-identified and no individual participant identifiers will be used in presentations of study results and publications.

The OSU Information Technology (IT) Department will provide web-based resources such as instructions for connecting to Zoom®, and support to address other technological challenges such as Wi-Fi connectivity. For participants who do not have a Wi-Fi-enabled device or Wi-Fi access, a Wi-Fi enabled device such as a tablet and or Wi-Fi connectivity will be provided to them for the time required for their study participation. If needed, participants will be put in touch with a College of Nursing IT specialist ([name] or another representative) for any technical assistance that is needed. The OSU Center for Clinical and Translational Research Community Connectors Program will assist with social media recruitment and REDCap setup for data collection. Partnership will continue with the local AAAWA and Alzheimer's Association for recruitment and future intervention implementation. Available community-based financial assistance for reduced Wi-Fi cost will be recommended for caregivers who request Wi-Fi access. Pair 2 Care framework implemented into existing programs such as AAAWA and scaled for adaptation to other caregiver types and racial/ethnic groups ensures sustainability. Policy development ensures inclusion in local, state, and national caregiver programs. Additional potential barriers and solutions are proposed in Table 5.

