## K. Data Analysis

Descriptive statistics will be conducted on all participant demographic data using SPSS® or similar software.

Aim 1: Feasibility and acceptability of the Pair 2 Care Intervention in current ( $n=15$ ) and trained former ( $n=15$ ) African American ADRD family caregivers will be determined by our eligibility criteria, recruitment, and retention data (e.g., consent, drop out, refusal rates), protocol adherence, satisfaction, and appropriateness of the intervention for broader dissemination. We will conduct descriptive statistics for this Aim using proportion for categorical measures (recruitment, retention, and protocol adherence) and mean±standard deviation for continuous measures (80% satisfaction and 80% appropriateness). Interviews will be conducted with current caregivers to gather in-depth data on their Pair 2 Care Intervention experiences, including feedback on the likelihood of the intervention meeting the needs of African American ADRD caregivers. Interviews will be analyzed as described below. Aim 2: Descriptive statistics will be used to summarize sample characteristics and outcome measures (anxiety, depression, quality of life, social support, self-efficacy for surrogate decision making, and intent to use palliative care/hospice services) at each time point. For each outcome, we will use mixed-effects linear modeling for repeated measures to model the outcome as a linear function of fixed-effect of time. The model will also include subject-specific random intercepts to adjust for within-subject clustering from repeated measures. We hypothesize that at 6 months as compared to baseline, current caregivers will report less anxiety and depression, higher quality of life, higher social support, higher self-efficacy for surrogate decision making, and higher intent to use palliative care/hospice services. From the mixed-effects modeling, we will test this hypothesis by deriving contrast estimate of change of outcome between baseline and 6 months.

Power analysis suggested that our sample size ( $n=15$ ) will have only 38% power to detect a medium effect size of Cohen's  $d = 0.5$  for outcome change from baseline at 6 months. This effect size is equivalent to a clinical meaningful difference. Therefore, we will not rely on statistical significance. Instead, results interpretation will be guide by point estimates, precision of the estimates (e.g., 95% confidence interval), effect sizes, and their clinical significance.

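### Does Section K need a rule for mentees who stay in the study after their mentor leaves?

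*Combined protocol and SAP*

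**What the plan says.** Section I (Study Risks) covers the case where one member of a pair leaves. The event is documented, and the text goes on: "the remaining peer may be given the option to remain in the study, and their data analyzed to reflect this change in their engagement". The next sentence reads: "Their data may be analyzed separately from peers that complete the full study". Both statements concern the remaining peer, who may be a mentor or a mentee.

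Section K (Data Analysis) sets out Aim 2. For each outcome a mixed model will "model the outcome as a linear function of fixed-effect of time". It continues: "The model will also include subject-specific random intercepts to adjust for within-subject clustering from repeated measures". The result of interest is the contrast of 6 months against baseline. Because the stated power is only 38%, significance is set aside and "results interpretation will be guide by point estimates, precision of the estimates (e.g., 95% confidence interval), effect sizes, and their clinical significance". The section has no pair-status term, subset or sensitivity analysis.

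On the data themselves, Section H says: "Current caregivers (mentees) will complete surveys in the beginning, 3 months, 6 months, and 1-month follow-up". Table 4 gives the retention benchmark: "Retain at least 70% of current and former caregivers". Section G notes: "Mentors may be assigned an additional mentee".

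**The concern.** Section I announces an analysis step that Section K does not contain. The wording is permissive and gives no criterion, so the choice between one combined analysis and a split one could be made with the results in view. With at most 15 mentees, and interpretation resting on estimates and intervals, who is in the contrast is part of the result. Broken pairs are also plausible: the benchmark tolerates 30% loss, and one mentor with two mentees could leave both unpaired.

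A side point concerns retention. If 70% is pooled over both roles, 21 of 30 could be reached with 9 mentees and 12 mentors, although only mentees supply Aim 2 outcomes.

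**Working it through.** **The plan's own figure.** The plan gives no number on this point. The 38% power in Section K is a separate matter. A two-sided paired t test at 0.05 (assumed) with n = 15 and a standardized change of 0.5 gives 43.8%; 13 evaluable mentees would give 38.2%. The plan does not state its alpha, correlation or dropout assumption, so the figure is unexplained rather than shown to be wrong. Nothing below uses it.

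**The two sections side by side.**

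| Question | Section I | Section K |
|---|---|---|
| Who is covered? | Remaining mentor or mentee | Mentees (Aim 2 outcomes) |
| Is a separate analysis required? | No, permitted | Not mentioned |
| Who is in the main contrast? | Not stated | No exclusion, so every mentee with data |

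No entry contradicts another. For a remaining mentor, Section I can bear only on Aim 1 and interview material, which Section K treats descriptively or qualitatively. For a remaining mentee, the model in Section K accepts the data without any special step.

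**Size, if the optional analysis replaced the main one.** These inputs are assumptions, not figures from the plan: 11 of 15 mentees complete all visits (0.70 × 15 = 10.5, rounded up), 4 give baseline only, 3 of the 11 lost their mentor, and the within-mentee correlation is 0.5. The visits are at 0, 3, 6 and 7 months (Sections G and H). Results are in SD of change, where SD of change = √(2(1 − ρ)) times the outcome SD. Degrees of freedom = observations − mentees − time parameters.

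For n completers the standard errors have simple forms:
- Categorical time: SE = √(1/n).
- Linear time: the visit times have mean 4 and squared deviations 16 + 1 + 4 + 9 = 30, so SE = √(36/(2 × 30 × n)) = √(0.6/n).

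With the baseline-only mentees included, the SE comes from generalized least squares under a random intercept.

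| Set | Time | SE | df | t | Half-width |
|---|---|---|---|---|---|
| 11 complete + 4 baseline-only | categorical | 0.2913 | 48 − 15 − 3 = 30 | 2.042 | 0.595 |
| 8 intact-pair completers | categorical | √(1/8) = 0.3536 | 32 − 8 − 3 = 21 | 2.080 | 0.735 |
| 11 complete + 4 baseline-only | linear | 0.2248 | 48 − 15 − 1 = 32 | 2.037 | 0.458 |
| 8 intact-pair completers | linear | √(0.6/8) = 0.2739 | 32 − 8 − 1 = 23 | 2.069 | 0.567 |

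Ratios: 0.735/0.595 = 1.24 and 0.567/0.458 = 1.24. Over correlations 0.3 to 0.7 the full-set half-width runs from 0.586 to 0.603 (categorical) and from 0.450 to 0.465 (linear); the completer values do not depend on the correlation. Keeping the 4 baseline-only mentees beside the 8 gives 0.704 and 0.540, about 18% wider. That set, however, is not the group of full completers that Section I names.

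The estimate would move by about 3/11 of the difference between intact-pair and broken-pair mentees. A difference of 0.25 SD (assumed) gives 3/11 × 0.25 = 0.07 SD, in either direction.

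These figures do not cover the palliative and hospice intent form, which Table 3 lists only at baseline and in the last column.

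**Retention.** Pooled, 0.70 × 30 = 21, which 9 + 12 or 10 + 11 would meet. Read as 70% of each group, at least 11 of 15 mentees are needed and both examples fail. Table 4 supports either reading.

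**The case for a change.** The strongest case for a change is that a default is not a rule. Section I allows departure from it without a criterion, and nothing in a model with time alone reflects a change in engagement. Since the plan interprets estimates and intervals, a single sentence fixing the analysis set would remove a choice that could be made after seeing the data, at almost no cost.

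It is true that Section K never names its analysis set and that the separate analysis carries no label. It does not follow that the planned analysis is at risk. Section K specifies the model and the contrast. Reporting only intact pairs as the main result would be a visible departure from it, because Section I also requires broken pairs to be documented. The promise to reflect the change in engagement can be met by reporting those pairs and, if wanted, showing their data beside the main result.

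The proposed sentence would therefore write down what an analyst would do anyway. A rule based on intact pairs would also raise a question of its own: a mentor may take a further mentee, so a re-paired mentee would have to be classed.

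Reporting retention by role is sensible, but it is a preference. Aim 1 already lists the two groups separately, and nothing prevents it.

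**Conclusion.** The concern does not call for a change. This is an omission of detail, not a contradiction, and the ordinary reading fills it: all mentees with data stay in the Aim 2 contrast, and any analysis by pair status is supplementary. The study is a declared pilot that is not fully powered and does not rely on significance.

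Replacing the main analysis with intact-pair completers would widen the interval by about 24% and could move the estimate by some 0.07 SD. Both figures rest on an assumed 3 of 11 completers losing their mentor; the shift also rests on an assumed 0.25 SD difference, and its direction is unknown. They show why the default is the better main analysis and reveal no fault in it. The conclusion assumes that Section K is followed as written.
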